3.5.1.3 Exploratory Pharmacodynamic Endpoint(s)

- [REDACTED]

- [REDACTED]
- [REDACTED]

11. **What is the primary purpose of the *Journal of Clinical Endocrinology and Metabolism*?**

3.5.1.4 Analysis of Exploratory Pharmacodynamic Endpoint(s)

Term	Percentage
GMOs	85%
Organic	80%
Natural	75%
Artificial	10%
GMOs	85%
Organic	80%
Natural	75%
Artificial	10%
GMOs	85%
Organic	80%
Natural	75%
Artificial	10%

3.6 Other Additional Analyses

3.7 Safety Analyses

All safety analyses will be based on the As-treated population. The primary safety endpoints are the safety and tolerability of MEDI5884 as measured by the incidence of TEAEs and TESAEs. Investigators are to record clinically important changes in physical examination, laboratory values, 12-lead ECGs, and vital signs as AEs. In addition, numeric values from clinical laboratory tests, ECGs and vital signs will be summarized descriptively. Other safety parameters, such as descriptive ECG readings and physical examination entries will be provided as listings.

The evaluations will be descriptive in nature, and observed differences will be evaluated for medical relevance. No formal statistical comparisons will be performed for the safety summaries.

3.7.1 Adverse Events and Serious Adverse Events

Treatment emergent AEs (TEAEs) and Treatment emergent serious AEs (TESAEs) are events that had an onset after the first dose of investigational product. TEAEs and TESAEs will be coded with the most updated version of the Medical Dictionary for Regulatory Activities (MedDRA), and the incidence, severity and relationship to investigational product will be summarized by treatment group and MEDI5884 overall for each MedDRA system organ class and preferred term reported. Adverse events leading to discontinuation, AEs leading to death, and deaths will also be summarized. Specific AEs will be counted once for each subject when calculating percentages. In addition, if the same AE occurs multiple times within a subject, the highest severity and level of relationship observed will be reported. All TEAEs and TESAEs will be summarized overall, as well as categorized by MedDRA system organ class and preferred term. Injection site assessments (redness, swelling, and pain) regardless reported as AEs or not will also be summarized.

Subjects with potential immunogenicity related TEAEs for immune complex diseases, allergic reactions, and injection site reactions according to Standardized MedDRA Queries (SMQ) will be summarized. The US Food and Drug Administration has requested that safety data be analyzed for this study according to the following SMQs: Systemic lupus erythematosus (broad and narrow terms); vasculitis (broad and narrow terms); Guillain-Barre syndrome (narrow terms) and allergic reactions (narrow SMQs for anaphylactic reaction, angioedema, severe cutaneous adverse reaction, anaphylactic/anaphylactoid shock conditions and hypersensitivity). Injection site reactions will be assessed using the following high level MedDRA (HLT) terms: administration site reactions, application and instillation site

reactions, infusion site reactions, and injection site reactions. These terms will be updated to the current version of MedDRA.

3.7.2 Adverse Events of Special Interest

The following AESI has been identified specifically for this protocol:

- Hepatic function abnormality meeting the definition of Hy's law

The AESIs will be summarized by treatment group and MEDI5884 overall, as well as by MedDRA system organ class and preferred term.

3.7.3 Deaths and Treatment Discontinuations due to Adverse Events

Death and AEs resulting in permanent discontinuation from the study drug will be summarized by treatment group and MEDI5884 overall as well as by MedDRA system organ class and preferred term.

3.7.4 Clinical Laboratory Evaluation

The hematology and serum chemistry parameters as well as their changes from baseline will be summarized with descriptive statistics by treatment group at each of the scheduled visits. In addition, hematology and serum chemistry values will also be classified as low, normal, or high with respect to the laboratory reference range for the parameter. The shift from baseline category to each post-baseline visit category for each parameter will be summarized at each post-baseline visit by treatment group as well as for MEDI5884 overall.

The urinalysis categorical results will be classified as normal or abnormal with respect to the laboratory reference range for the parameter. The shift from baseline category to the post-baseline category will be summarized by treatment group and MEDI5884 overall at each post-baseline visit.

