2 OBJECTIVES AND ENDPOINTS

2.1 Primary Objective and Associated Endpoint

Table 2.1-1 Primary Objective and Associated Endpoints

Type	Objective	Endpoint
Safety	Evaluate the safety and tolerability of repeated [REDACTED] dosing with MEDI5884 in subjects with stable CHD	
• Occurrence of TEAEs and TESAEs and clinically important changes in ECGs, vital signs, clinical laboratory evaluations and physical examination up to end of study ([REDACTED])

CHD = coronary heart disease; ECG = electrocardiogram; TEAE = treatment-emergent adverse events; TESAE = treatment-emergent serious adverse events

[figure not shown]

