4.2.2.1 Early Discontinuation Visit or Unscheduled Study Visit

Study procedures should be completed as per [REDACTED]/early discontinuation visit for subjects who prematurely discontinue from the study and for subjects who require an unscheduled study visit. Subjects should be encouraged to remain in the study for follow-up.

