4.3.3 Clinical Laboratory Tests

A laboratory manual will be provided to the sites that specifies the procedures for collection, processing, storage, and shipment of samples, as well as laboratory contact information, specific to this clinical research study.

Clinical laboratory safety tests, including urine pregnancy tests, will be performed in a licensed clinical laboratory. Urine pregnancy test will be conducted at Screening and on [REDACTED] Urine pregnancy tests may be performed at the site using a licensed test (dipstick). Clinically significant (as determined by the investigator) abnormal laboratory results should be repeated as soon as possible (preferably within 24 to 48 hours).

The following clinical laboratory tests will be performed:

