4.8.3.2 Analysis of Clinical Laboratory Parameters, Vital Signs, and Electrocardiograms

Clinical laboratory data and vital signs will be summarized at each time point by treatment group. Change from Baseline to each postbaseline time point in these data will also be summarized, where appropriate. ECG parameters will also be assessed and summarized by treatment group descriptively.

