10.5.3 Identification of Potential Hy's Law Cases

In order to identify cases of potential Hy's Law, it is important to perform a comprehensive review of laboratory data for any subject who meets any of the following identification criteria in isolation or in combination:

- ALT $\geq 3 \times$ ULN
- AST $\geq 3 \times$ ULN
- TBL $\geq 2 \times$ ULN

In cases where a subject may meet any of the abnormal laboratory identification criteria, in isolation or in combination, the central laboratory will immediately send an alert to the investigator (also sent to sponsor study representative).

The investigator will also remain vigilant for any local laboratory reports where the identification criteria are met, where this is the case the investigator will:

- Notify the sponsor study representative
- Request a repeat of the test (new blood draw) by the central laboratory
- Complete the appropriate unscheduled laboratory case report form (CRF) module(s) with the original local laboratory test result

When the identification criteria are met from central or local laboratory results the investigator will without delay:

- Determine whether the subject meets potential Hy's Law criteria (see Section 10.5.2) by reviewing laboratory reports from all previous visits (including both central and local laboratory results)

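### SAP 3.7.4 summarizes hematology and chemistry only visit by visit: no once-per-subject worst-value table by arm, and no rule for unscheduled, repeat or local results

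*SAP*

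**What the plan says.** SAP Section 3.7.4 has two outputs for hematology and serum chemistry. Values and changes from baseline "will be summarized with descriptive statistics by treatment group at each of the scheduled visits". Each value is also classed as low, normal or high, and the shift from the baseline category "will be summarized at each post-baseline visit by treatment group as well as for MEDI5884 overall". Protocol Section 4.8.3.2 is no more specific: "Clinical laboratory data and vital signs will be summarized at each time point by treatment group".

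The protocol also produces laboratory results away from the regular visit grid:

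- Section 4.2.2.1 sets out procedures "for subjects who prematurely discontinue from the study and for subjects who require an unscheduled study visit". Both follow a named early-discontinuation column of the schedule whose label is partly redacted.
- Section 4.3.3 says that clinically significant "abnormal laboratory results should be repeated as soon as possible (preferably within 24 to 48 hours").
- Section 10.5.3 covers local liver results that meet the identification criteria. The investigator is to "Complete the appropriate unscheduled laboratory case report form (CRF) module(s) with the original local laboratory test result".

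The primary endpoint in Protocol Section 2.1 includes the occurrence of "clinically important changes in ECGs, vital signs, clinical laboratory evaluations and physical examination up to end of study". SAP Section 3.7 measures primary safety by the incidence of treatment-emergent adverse events (TEAEs) and their serious subset, and adds: "Investigators are to record clinically important changes in physical examination, laboratory values, 12-lead ECGs, and vital signs as AEs".

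**The concern.** The safety question for laboratory data has the form: how many subjects in each arm had an abnormal value at any time after dosing began? A set of by-visit tables does not answer it. Results drawn because something looked wrong are informative for that question, and the SAP does not say which table, if any, they enter.

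At stake is the systematic comparison between arms for every hematology and chemistry parameter. With small arms, a reader would otherwise have to rebuild it from listings, subject by subject.

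**Working it through.** No sample-size, power or error-rate figure is involved, and the plan states no number to reproduce. The check is a reading of which records enter which table, plus one bound.

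**1. Time basis of each output.** The word scheduled qualifies only the descriptive statistics. The shift tables refer to post-baseline visits without that word, so early-discontinuation and unscheduled visits are neither named nor excluded there. Both outputs are nevertheless indexed by visit, and neither has a row for the worst value over the study.

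**2. Rules for records off the grid.** SAP Section 3.1 defines baseline and limits what may be carried forward. It has no visit windows, no choice between a first and a repeat value at the same visit, and no rule for unscheduled or local results. Section 3.7.4 adds none. By source:

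- Early discontinuation: could be tabulated under its own named visit, but the SAP does not say so.
- Unscheduled visit: same procedures as early discontinuation; no table assignment stated.
- Repeat draw: no assignment stated. If the first value came from a scheduled draw, that value is already tabulated.
- Local result: captured in the CRF; no assignment stated. Section 10.5.3 concerns only ALT, AST and total bilirubin.

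**3. Can by-visit counts give the any-time count?** Let a(v) be the number of subjects in one arm with an abnormal value at visit v, and N the number abnormal at one or more visits. Then

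largest a(v) ≤ N ≤ the smaller of 20 and the sum of all a(v).

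The lower bound is reached when the same subjects recur, the upper when they are all different. By-visit tables do not show which applies. As an invented illustration, suppose one abnormal subject at each of two visits in an arm of 20. N is then 1 (1/20 = 5%) or 2 (2/20 = 10%), and the tables look the same. This needs only more than one post-baseline chemistry draw. The schedule in Protocol Table 4.2.2-1 shows that, although its columns are imperfectly extracted. The point holds even if every record is scheduled.

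**4. Comparison within the SAP.** Section 3.7.4.3 counts subjects by maximum QTcF, QTcB and QT, and by maximum change from baseline in QTcF and QTcB. The once-per-subject extreme is therefore already part of the SAP's approach to safety data. Laboratory data have no counterpart.

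**5. Other by-arm routes.** TEAEs are tabulated by arm and for MEDI5884 overall, with each event counted once per subject (SAP Section 3.7.1). Hy's law cases are tabulated as adverse events of special interest (Section 3.7.2). Data are listed by treatment group and subject (Section 3.1). The first route depends on each investigator's judgment across about 25 sites, the second covers only cases that meet the Hy's law definition, and the third is not a summary.

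**6. Scale.** Protocol Section 3.1.2 has 20 subjects per arm, so one subject is 1/20 = 5 percentage points. The documents do not say how many subjects would have their only abnormal value off the grid.

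**The case against.** The strongest reply is that the SAP already has an any-time, per-subject, by-arm count of clinically important laboratory changes: the TEAE tables. Investigators record such changes as adverse events whichever draw revealed them. A low/normal/high shift measures something different, namely a crossing of the reference range. This stands. A reader might infer that the by-visit tables undercount the primary endpoint, but the documents do not support that, because SAP Section 3.7 measures primary safety through adverse events.

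A reader might also infer that off-schedule results are shut out of every laboratory table. That is not supported either. The shift tables are not limited to scheduled visits, and early discontinuation has a named column. Subjects who stop investigational product stay on protocol assessments unless they withdraw consent (Protocol Section 4.1.6), so stopping treatment does not by itself end scheduled draws. What the text supports is silence about assignment, which is weaker than exclusion.

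Nor should the gap be sized by how often a short-lived abnormality falls between draws. Most such abnormalities would never be sampled, and no table can recover a value that was not drawn.

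Finally, SAP Section 3.6 has no visible text, and Section 1 leaves table templates to a statistical programming plan that is not among the documents. A worst-value table or an assignment rule could be in either. This also stands, as a limit on the finding.

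None of these replies supplies, in the visible text, a systematic by-arm laboratory summary that counts each subject once.

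**Conclusion.** The point holds as a gap in the laboratory summaries and a cheap improvement. SAP Section 3.7.4 has no once-per-subject summary of worst post-baseline hematology and chemistry values by arm, and gives no rule for unscheduled, repeat or local results. It is also silent on whether early-discontinuation results are tabulated under their own visit. The first part follows from the by-visit structure alone and does not depend on how a post-baseline visit is read.

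Its size cannot be given beyond the scale of one subject per 5 percentage points of an arm. The conclusion assumes that neither SAP Section 3.6 nor the programming plan already contains an equivalent table. The adverse-event route, the Hy's law table and the listings limit the consequence.

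**What to change.** Keep the by-visit tables and add to SAP Section 3.7.4:

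- A shift from baseline category to worst post-baseline category, lowest and highest separately, for each hematology and chemistry parameter. Count each subject once, by treatment group and for MEDI5884 overall.
- A sentence stating that this table uses every post-baseline record containing the parameter: scheduled, early-discontinuation, unscheduled, repeat, and local results with a recorded reference range.
- A sentence stating how early-discontinuation, unscheduled, repeat and local results are treated in the by-visit tables.
- The number of draws per subject, by arm.

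The cost is a table shell and a few sentences, with no new data. The small downside is that subjects with more draws have more chances to show an abnormal value. The draw counts let the reader see whether that differs between arms.

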4.1.3 Exclusion Criteria

Any of the following would exclude the subject from participation in the study:

1. Unstable cardiovascular conditions, including acute coronary syndrome, stroke or transient ischemia attack, critical limb ischemia, arterial revascularization, life-threatening arrhythmias, or heart failure hospitalization within [REDACTED] of Screening
2. Any planned arterial revascularization (coronary, peripheral or carotid)
3. New York Heart Association Class III or IV congestive heart failure or treatment with advanced therapies (cardiac transplant, ventricular assist device, cardiac resynchronization therapy, and/or chronic intravenous ionotropic support)
4. Severe valvular heart disease
5. Fasting laboratory values at Screening for any of the following:
 - a. Triglycerides >500 mg/dL
 - b. LDL-C >100 mg/dL (by direct measure)
6. Clinically significant BP abnormalities at Screening after 10 minutes supine rest:
 - a. Systolic BP <90 or >160 mmHg
 - b. Diastolic BP >100 mmHg

Note: BP may be retested one time at the discretion of the investigator.
7. ECG results from the central lab report at Screening, demonstrating:
 - a. Prolonged QTcF >460 milliseconds based on reported mean of any ECG, or
 - b. QRS >160 milliseconds based on reported mean of any ECG
8. Family history of long QT, or any clinically significant ECG finding as judged by the investigator (at [REDACTED]) that may interfere with the interpretation of serial ECG and QT interval changes
9. Current or previous use of lipid-lowering medications within [REDACTED] prior to Screening, except for statins and/or <100-mg/day niacin, and/or 10-mg/day ezetimibe, and/or <2-g/day fish oil
10. History of any of the following:
 - a. Documented genetic disorder of cholesterol metabolism
 - b. Chronic kidney disease stage 4-5, defined by estimated glomerular filtration rate <30 mL/min/1.73 m² by the modification of diet in renal disease equation, or end stage renal disease treated with kidney transplant or renal replacement therapy
 - c. History of clinically overt chronic liver disease or biochemical evidence of liver disease (eg, aspartate transaminase [AST] or alanine transaminase [ALT] >1.5 × upper limit of normal [ULN] and/or total bilirubin [TBL] >ULN [unless due to Gilbert's syndrome])
 - d. Poorly controlled endocrine disorder including Type 1 or Type 2 diabetes mellitus with glycated hemoglobin >10% as assessed at Screening

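### The by-arm urinalysis table in SAP 3.7.4 uses only normal/abnormal for categorical results, so worsening in a subject already abnormal at baseline looks the same as stability

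*SAP*

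**What the plan says.** SAP 3.7.4 (Clinical Laboratory Evaluation) sets the rule for categorical urinalysis: "The urinalysis categorical results will be classified as normal or abnormal with respect to the laboratory reference range for the parameter". It then names the output: "The shift from baseline category to the post-baseline category will be summarized by treatment group and MEDI5884 overall at each post-baseline visit".

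The same section gives the other laboratory panels more: "The hematology and serum chemistry parameters as well as their changes from baseline will be summarized with descriptive statistics by treatment group". Those panels also get low/normal/high shifts. Vital signs (SAP 3.7.4.2) and ECG (SAP 3.7.4.3) have change from baseline, and ECG has graded thresholds as well.

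The protocol's primary endpoint (Section 2.1) includes "clinically important changes in ECGs, vital signs, clinical laboratory evaluations and physical examination", and urinalysis is one of the clinical laboratory tests (Section 4.3.3.3). SAP 3.7 expresses the primary safety measure in terms of adverse events: "The primary safety endpoints are the safety and tolerability of MEDI5884 as measured by the incidence of TEAEs and TESAEs". It asks investigators to record clinically important laboratory changes as AEs, promises descriptive summaries of numeric laboratory values, and rules out formal comparisons of safety data. SAP 3.1 provides listings by treatment group and subject.

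**The concern.** A two-class shift table has one cell for subjects who are abnormal at both visits. It cannot show whether they stayed the same, improved within the abnormal range, or worsened. For hematology and chemistry, the change-from-baseline summaries compensate for this. For categorical urinalysis, SAP 3.7.4 specifies nothing comparable.

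Eligibility does not rule out such subjects. The renal exclusion in Protocol 4.1.3 is "Chronic kidney disease stage 4-5, defined by estimated glomerular filtration rate" below 30, and the diabetes exclusion applies to "mellitus with glycated hemoglobin >10% as assessed at Screening". No criterion names a urinalysis result. A 45- to 80-year-old with CHD and less advanced kidney disease, or with diabetes below that cut-off, may therefore enter with an abnormal dipstick.

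What is at stake is an arm-level pattern. Small increases in urinary protein or blood might not prompt an AE report in any one subject, yet could be visible when counted across an arm. The readable test lists in Protocol 4.3.3 contain no other urinary protein or blood measure.

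**Working it through.** The plan states no figure on this point, so there is none to reproduce. The check has two parts: the logic of the table, and the number of subjects it could concern.

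**1. What the two-class table can show.** The documents give no dipstick scale, so assume four ordered levels (negative, 1+, 2+, 3+) with negative as normal.

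- Possible worsening transitions: 4 × 3 / 2 = 6.
- Visible as normal to abnormal: negative to 1+, 2+ or 3+, which is 3.
- Not visible, because both ends are abnormal: 1+ to 2+, 1+ to 3+, 2+ to 3+, which is 3 × 2 / 2 = 3.

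A shift table on the four levels would show all 6. These are counts of table cells, not of subjects, so they do not mean that half of all worsening is hidden.

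**2. How many subjects could be affected.** Inputs: 20 subjects per cohort and six cohorts (Protocol Table 3.1.2-1); up to five dose levels against placebo (SAP 2.2), hence 5 × 20 = 100 active subjects; and an assumed proportion p abnormal at baseline for a given analyte. The expected number per arm is 20 × p. The chance that an arm contains at least one such subject is 1 − (1 − p)^20.

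| Assumed p | Expected per arm of 20 | Expected among 100 active | Chance of at least one in an arm |
|---|---|---|---|
| 5% | 1 | 5 | 1 − 0.95^20 = 64% |
| 10% | 2 | 10 | 1 − 0.90^20 = 88% |
| 20% | 4 | 20 | 1 − 0.80^20 = 99% |
| 30% | 6 | 30 | 1 − 0.70^20 > 99% |

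These are subjects in whom worsening could not show in the table, not subjects expected to worsen.

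**3. Where the same worsening could still appear.**

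- Judged clinically important by the investigator: recorded as an AE (SAP 3.7) and tabulated by treatment group and MEDI5884 overall (SAP 3.7.1).
- Reported as a number, as pH or specific gravity might be: covered by the descriptive summary of numeric laboratory values in SAP 3.7, although 3.7.4 does not repeat this for urinalysis.
- Any other categorical worsening within abnormal: subject-level listings only.

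The last line is the gap.

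**The case against.** The strongest reply is that the protocol's endpoint concerns clinically important changes, not every step on a dipstick, and that the SAP has a by-arm route for those changes through AE reporting. This stands, and it sets the limit of the point. A reader might infer that part of the primary endpoint goes unanalyzed, or that urinalysis has no other by-arm route. The documents do not support either reading. What the AE route does not provide is a count of changes that each investigator, seeing one subject at a time, did not think worth reporting.

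A reader might also infer that graded results are collected and then thrown away. Protocol 4.3.3.3 lists analytes without a reporting scale. The laboratory manual and the statistical programming plan, which is to hold the table templates, are separate documents. Whatever is reported will be listed.

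The eligibility argument is also weaker than criteria 10b and 10d alone suggest. Criterion 10j allows exclusion for any laboratory value that the investigator or medical monitor considers an unacceptable risk or an obstacle to evaluation. That is discretionary and does not remove every abnormal baseline urinalysis, but it may reduce the number.

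Finally, serum creatinine, urea nitrogen and albumin are scheduled alongside urinalysis and are summarized with change from baseline. They do not measure urinary protein or blood, but they soften the consequence.

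**Conclusion.** The point holds as a minor gap in a descriptive safety table. For categorical urinalysis results, the by-arm table specified in SAP 3.7.4 cannot separate worsening from stability in a subject already abnormal at baseline, and the part not reported as an AE has no other by-arm display in the SAP.

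The table's limitation follows from the SAP wording alone. Its practical size rests on assumptions: that the laboratory reports some analytes in ordered categories, and that some enrolled subjects are abnormal at baseline. At an assumed 5% to 30%, that is 1 to 6 subjects per arm of 20 for a given analyte.

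A reader might be tempted to express the loss as reduced power to detect a difference between arms. The documents do not support that: SAP 3.7 plans no formal safety comparison, and neither a baseline prevalence nor a worsening rate is given. No estimate, error rate or sample size is affected. This is a cheap improvement, not a defect in the trial's main conclusions.

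**What to change.** In SAP 3.7.4, for each analyte that the central laboratory reports in ordered categories (for example protein, blood, glucose, ketones and leukocyte esterase):

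- tabulate the shift from baseline on the reported categories, by treatment group and MEDI5884 overall;
- add one row with the number and percentage of subjects whose worst post-baseline category is above their baseline category.

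Keep the normal/abnormal shift where that is all the laboratory reports. Confirm the reporting scale with the laboratory before fixing the table shells.

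The cost is a wording change and somewhat longer tables, with no added assessments or samples. Cells will be sparse in arms of 20; the single worsening row per analyte keeps the result readable.
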